IRB	Institutional Review Board

MCP	Monocyte chemoattractant protein
MHC	Major histocompatibility complex
NKR	Natural killer receptors
OCT	Optical coherence tomography
RF	Rheumatoid factor
PI	Principal investigator
RAU	Recurrent anterior uveitis
SAE	Serious adverse event
SUN	Standardization of Uveitis Nomenclature
TNF-α	Tumor necrosis factor-alpha
UAR	Relapsing autoimmune uveitis
VZV	Varicella-zoster virus

Protocol Synopsis

TITLE SPONSOR	Assessment of the anti-inflammatory effects of NORFLO [®] ORO in acute relapses of HLA-B27-associated autoimmune uveitis: a multicenter randomized, placebo-controlled, double-blind clinical study. Eye Pharma SpA, [name] [contact] – [contact]
NUMBER OF SITES	4
RATIONALE	In our previous study, [name] et al. have shown how the treatment with NorFlo [®] (curcumin-phospholipid (Meriva [®] 600mg)) 2 tablets daily in 128 patients in combination with conventional therapy is capable of reducing the relapses in patients with recurrent anterior uveitis (RAU) by 88%. The enrolled subjects suffered from uveitis of different etiologies, among which were found three main different etiological groups: herpetic uveitis, autoimmune inflammatory ocular disease and various origin anterior uveitis. Among these three groups, the most sensitive patients to the treatment were autoimmune RAU (n=56). These extraordinary results lay the groundwork for further investigating the effectiveness of curcumin-phospholipids in autoimmune HLA-B27-associated uveitis, which represents the most common type of uveitis (75% of total uveitis). NORFLO [®] ORO aims at obtaining an anti-inflammatory effect that is synergistic to conventional therapy to counteract the occurrence of secondary symptoms (as cystoid macular edema) of HLA-B27-associated uveitis.
STUDY DESIGN	This is a multicenter, randomized, double-blind, placebo-controlled study.
PRIMARY OBJECTIVE	To explore the efficacy of NORFLO [®] ORO in reducing the number and severity of relapses, when compared to placebo. The reduction of the mean number of relapses per patient between the year before study treatment and the study period will also be assessed.

SECONDARY	- To evaluate the improvement of side effects due to HLA-B27-
OBJECTIVES	associated uveitis such as glaucoma, cystoid macular edema,
	keratopathy and synechia.
	- To evaluate the improvement in uveitis-related symptoms.
	- To evaluate cell damage and inflammation reduction in patients
	with HLA-B27-associated uveitis.
	- To evaluate the patients' attitude towards the study treatment.
	- To evaluate the safety profile of the study product.
NUMBER OF	60
SUBJECTS	
SUBJECT	Inclusion Criteria:
SELECTION	1. Subjects ≥ 18 years of age at baseline Visit.
CRITERIA	2. HLA-B27 positive related uveitis (acute alternating non
	granulomatous uveitis); the uveitis shall not be in acute phase at
	the time of enrolment and at least 8 weeks must have elapsed after
	the resolution of the last uveitis attack.
	3. Subjects with at least one autoimmune uveitis relapse (UAR) in the
	last year.
	4. Written informed consent obtained from subject or subject's legal
	representative and ability for the subject to comply with the
	requirements of the study.
	Exclusion Criteria:
	1. Presence of a condition or abnormality that in the opinion of the
	investigator would compromise the safety of the patient or the
	quality of the data collected.
	2. Subjects that have received systemic therapy for uveitis with anti-
	inflammatory, immunosuppressive or biological drugs in the 30
	days before study start.
	3. Subjects with an anticipated need for systemic anti-inflammatory,
	immunosuppressive or biological drugs during the 12 months of
	the study.
	4. Subjects who received an intravitreal, peribulbar, sub-tenon,
	periocular injection in the previous 6 months.
	5. Subjects that are receiving long-term treatment with systemic anti-
	inflammatory, immunosuppressive or biological drugs for other
	diseases different from uveitis.
	6. Women who are taking hormonal contraceptives.

	7. Subjects that have taken supplements and nutraceuticals in the
	last 30 days prior to baseline visit. Use of supplements and
	nutraceuticals will not be admitted during the study.
	8. Subjects for whom baseline LFM and other evaluations cannot
	be accurately performed.
	9. Women who are pregnant or breast-feeding.
TEST PRODUCT,	NORFLO [®] ORO at 2 single foil pouches per day (equal to 3.49 g of
DOSE AND ROUTE	product). The product will be administered orally every day for 12
OF	months. The administration will take place each day in two separate
ADMINISTRATION	doses before meals (lunch and dinner).
CONTROL	PLACEBO at 2 single foil pouches per day (equal to 3.49 g of product).
PRODUCT, DOSE	The product will be administered orally every day for 12 months. The
AND ROUTE OF	administration will take place each day in two separate doses before
ADMINISTRATION	meals (lunch and dinner).
DURATION OF	Subjects will participate in the study for up to 12 months.
SUBJECT	Treatment duration: 12 months
PARTICIPATION	Visits: Baseline Visit (Visit 1 - T ₀), Visit 2 (T ₁ , 6 months), Visit 3 (T ₂ ,
AND DURATION OF	12 months).
STUDY	
	The screening will be done in the same day of the baseline visit.
	After the first 3 months of treatment subjects will be contacted by phone
	by the study staff, to assess the correct study product intake.
	The enrolment period will be 3 months, therefore the total duration of
	the study is expected to be about 15 months.

CONCOMITANT	Allowed:				
MEDICATIONS	In case of relapse the following treatments will be allowed:				
	- any midriatic topical therapy				
	- any traditional topical therapy recommended for the treatment of				
	relapsing autoimmune uveitis.				
	In the case of relapse with LFM values are > 100 ph/ms despite treatment with topical therapy, or in any case the LFM values result to be > 100 ph/ms, then a systemic therapy is recommended and the subject has to be dropped-out from the study and treated according to the best medical judgement				
	Prohibited				
	Supplements and nutraceuticals; systemic therapies for uveitis with anti-inflammatory, immunosuppressive, biological drugs; hormonal contraceptives; long-term treatment with systemic anti-inflammatory, immunosuppressive or biological drugs for other diseases different from uveitis.				
	Systemic therapies with anti-inflammatory, immunosuppressive drugs are allowed for reasons different from uveitis and in any case for periods not exceeding 15-30 days.				
EFFICACY	A clinical assessment and diagnosis will be performed on each patient				
EVALUATIONS	enrolled in the study.				
PRIMARY ENDPOINT	Mean number per patient and severity of relapses reduction in the NORFLO [®] ORO treatment group when compared to the placebo group. The reduction of the mean number of relapses per patient between the year before treatment and the study period within each treatment group will also be assessed. The two endpoints will be assessed in a hierarchical order. Cell damage and inflammation reduction, as assessed by Laser Flare Meter in the NORFLO [®] ORO treatment group when compared to the placebo group.				

SECONDARY	The improvement of side effects due to HLA-B27-associated uveitis,
ENDPOINTS	such as intraocular pressure (IOP) by Goldmann applanation
	tonometry, cystoid macular edema (central foveal thickness – central 1
	mm subfield thickness) by optical coherence tomography (OCT)
	Spectralis [®] (Heidelberg Egineering, Heidelberg Germany),
	keratopathy, evaluated by fluorescein staining of the cornea, and
	synechia assessed by photographic slit lamp (anterior chamber
	photographs will be retained), in the NORFLO [®] ORO treatment group
	when compared to placebo group.
	The improvement in uveitis-related symptoms (BCVA, ocular pain,
	photophobia, floaters and blurred vision measured by VAS).
	Patients' attitude towards NORFLO [®] ORO treatment compared to
	placebo, through the Quick Questionnaire.
SAFETY	Incidence of adverse events in the NORFLO [®] ORO treatment group
EVALUATIONS	compared to placebo group.
	Use of concomitant medication.
	Changes in vital signs.
STATISTICS	Mean and standard deviation will be used to describe the number of
Primary Analysis	relapses per patient. The mean number of relapses per patient will be
	compared between the treatment groups using Student's t-test.
	ANOVA will be used to adjust for predictive/confounding variables.
	In addition, a generalized linear mixed model (GLMM) will be used to
	assess the effects of the treatment on reducing the number of relapses.
	The average and the maximum intensity will be compared between
	treatment groups using Student's t-test. ANOVA will be used to include
	predictive/confounding variables in the model.
	The mean number of relapses per patient observed during the study will
	be compared to the mean number of relapses reported during the
	previous year within each treatment group using paired t-test or
	ANOVA, to eventually adjust for predictive/confounding variables.
	The two endpoints will be assessed in a merarchical order.
Secondary Analysis	The incidence of side effects associated HI A-R27-associated uveitis
	such as IOP cystoid macular edema keratonathy and synechia will be
	compared between treatment groups using logistic regression
	The changes in BCVA and symptoms measured by VAS will be
	\mathbf{T} THE CHAIRSES IN DEVELOPMENT SYMPLETICES INCASINGLE DV VASS WITH THE
1	compared between treatment groups using ANCOVA, with the baseline

	The level of cell damage and inflammation will be assessed through				
	Laser Flare Meter. The difference between treatment groups will be				
	compared using ANCOVA, with the baseline level included in the				
	model				
	Each information collected through the Quick questionnaire will be				
	compared between the two treatment groups using chi-square test				
	compared between the two treatment groups using em-square test.				
Safety Analysis	Adverse event will be coded using the last updated version of the				
	Medical Dictionary for Regulatory Activities (MedDRA) dictionary to				
	give a preferred term (PT) and a system/organ class term (SOC) for				
	each. Adverse events will be tabulated by treatment group. Tables will				
	include the number of patients who experienced at least one AE, of				
	study product-related AEs (defined as definitely, probably, possibly, or				
	unrelated) of serious AFs, and the number of natients withdrawn due				
	to AE, summarized by treatment arm. Comparisons between treatment				
	arms will be performed using chi-square test. Concomitant medications				
	will be summarized by treatment using descriptive statistics and they				
	will be listed. Vital signs will be summarized by treatment using				
	descriptive statistics for shashing values and shares from baseling				
	descriptive statistics for absolute values and change from baseline.				
	Compliance to the study treatment will be assessed through the patient				
	diary and checked versus the used and unused study product containers				
	given back by the patients.				
Rationale for Number	With a statistical power of 80%, a significance level (alpha) of 5% and				
of Subjects	a common SD of 0.7, 46 patients are needed to observe a difference of				
	0.6 relapses/patients between the two treatment groups (2				
	relapses/patient in the NORFLO [®] ORO treatment group vs. 2.6 in the				
	placebo treatment group). To take into account a potential dropout rate				
	of 20% over 1 years, 60 patients will be recruited. A second primary				
	endpoint, i.e. the reduction of mean number of relapses between the				
	vear before treatment and the study period will be examined. These				
	two endpoints will be assessed in a hierarchical order				
	two enupoints will be assessed in a incratement order.				

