7.1 Allowed Medications and Treatments

All topical drugs (any topical midriatic treatment and any traditional topical therapy for uveitis) will be admitted for the treatment of the signs and symptoms associated with HLA-B27-associated chronic relapsing uveitis.

In the case of relapse with LFM values are > 100 ph/ms despite treatment with topical therapy, or in any case the LFM values result to be > 100 ph/ms, then a systemic therapy is recommended and the subject has to be dropped-out from the study and treated according to the best medical judgement.

7.2 **Prohibited Medications and Treatments**

The following medications are prohibited during the study and the administration will be considered a protocol violation: supplements and nutraceuticals, systemic therapies for uveitis (anti-inflammatory, immunosuppressive, biologicals), hormonal contraceptives, long-term treatment with systemic anti-inflammatory, immunosuppressive or biological drugs for other diseases different from uveitis. Systemic therapies with anti-inflammatory, immunosuppressive drugs are allowed for reasons different from uveitis and in any case for periods not exceeding 15-30 days.

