9.1.5 Urine dipstick specific pregnancy test

Urine dipstick specific pregnancy test will be performed at the site at baseline and at each following visit. The study products cannot be administered if the pregnancy test results positive or doubtful.

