10 EVALUATIONS BY VISIT

10.1 Visit 1 (t₀)

- 1. Review the study with the subject (subject's legal representative) and obtain written informed consent
- 2. Assign a unique screening number to the subject
- 3. Record subject's demographics data
- 4. Record subject's medical history, including a history of uveitis, diagnosis date and prior uveitis treatments and the number of relapses during the previous year
- 5. Record subject's concomitant medications
- 6. Perform a physical examination of the subject
- 7. Vital signs collection
- 8. Urine dipstick specific pregnancy test
- 9. Perform a rheumatologic evaluation of the subject
- 10. Perform subject's ophthalmic evaluation (BCVA, Slip lamp, OCT Spectralis[®], LFM, Goldman tonometry).
- 11. Evaluation of uveitis symptoms by VAS (ocular pain, blurry vision, floaters, photophobia)
- 12. Evaluation of the patient's attitude towards the study treatment, through the Quick Questionnaire
- 13. Evaluate inclusion/exclusion criteria adherence
- 14. Randomize subject and dispense study product
- 15. Initiate subject diary.

After about 3 months of treatment the study staff will contact the patient by phone to verify that the study product is correctly taken.

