10.2 Visit 2 (t_1 , 6 Months \pm 10 days)

- 1. Perform subject's ophthalmic evaluation (BCVA, Slip lamp, OCT Spectralis[®], LFM, Goldman tonometry)
- 2. Evaluation of uveitis symptoms by VAS (ocular pain, blurry vision, floaters, photophobia)
- 3. Perform a physical examination of the subject
- 4. Vital signs collection
- 5. Urine dipstick specific pregnancy test

- 6. Record any Adverse Event
- 7. Review subject's diary for Adverse Events and for dosing compliance
- 8. Study product collection and accountability
- 9. New diary and study product delivery
- 10. Concomitant medications review
- 11. Evaluation of the patient's attitude towards the study treatment, through the Quick Questionnaire

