10.4 Additional Unscheduled Visits in Case of Relapse

Should a relapse occur, an unscheduled visit will be performed including a complete ophthalmic evaluation. The number of cells in the AC will be determined by slit lamp, too.

Topical or systemic treatment will be prescribed to the subject according to the severity of the relapse and according to the best medical judgement.

Two following visits will be scheduled 2 and 6 weeks thereafter. During these visits a complete ophthalmic evaluation will be done.

If the subject is prescribed a systemic treatment for the relapse, he/she will be withdrawn from the study, and treated according to the best medical judgement.

If only topical treatments are prescribed, the subject will be allowed to continue the study. Depending on the onset time of the relapse it could be necessary to delay Visit 2 or Visit 3 around 2 months after the topical treatment conclusion.

Should Visit 2 be delayed, the delay will be recovered by keeping the date of Visit 3 at 12 months.

Should Visit 3 be delayed, the delay will not be recovered.

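### Women without a relapse have no planned pregnancy enquiry between visits about six months apart, although hormonal contraception is barred and product must stop on a positive test

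*Protocol*

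**What the plan says.** Exclusion criterion 6 (Protocol Synopsis and 6.3) reads "Women who are taking hormonal contraceptives". Section 7.2 carries the bar into the treatment year, naming hormonal contraceptives in a list that opens "The following medications are prohibited during the study and the administration will be considered a protocol violation". Criterion 9 excludes pregnant and breast-feeding women. The text available for review names no other contraceptive method.

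Section 9.1.5 sets the test and its consequence: "Urine dipstick specific pregnancy test will be performed at the site at baseline and at each following visit", and "The study products cannot be administered if the pregnancy test results positive or doubtful". According to SAP 1.2, protocol version 1.4 introduced the hormonal bar and the visit-based test together.

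The test is itemised at Visits 1, 2 and 3 (10.1 to 10.3 and Appendix 1). It carries over to early withdrawal because 10.5 repeats the Visit 3 activities as far as possible.

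Two kinds of contact can fall between scheduled visits:
- A telephone call: "After about 3 months of treatment the study staff will contact the patient by phone to verify that the study product is correctly taken". Appendix 1 gives it the same purpose.
- Relapse visits under 10.4: "Should a relapse occur, an unscheduled visit will be performed including a complete ophthalmic evaluation", and then "Two following visits will be scheduled 2 and 6 weeks thereafter". No pregnancy test is itemised there.

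Section 11.1 lists pregnancy among the possible reasons for stopping treatment.

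**The concern.** The sponsor has decided that pregnant women should not take the product and has made a test result the trigger for withholding it. It has also removed a class of contraception for a year. In a woman who keeps to schedule, only one test after baseline can interrupt dosing: the one at Visit 2. The Visit 3 test comes when treatment ends. Between visits the stop rule depends on the woman recognising a pregnancy and volunteering it, and the available text does not tell her to do so.

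If a pregnancy began soon after a visit and went unreported, daily dosing could continue for about six months against the sponsor's own rule. The issue is patient safety and consistency of conduct. No endpoint, analysis or sample size is involved.

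**Working it through.** **Inputs.** Visits at 0, 6 and 12 months, with ±10 days on Visits 2 and 3 (10.2, 10.3, Appendix 1). Call at about 3 months (10.1). Two pouches a day (8.4.1). Kits of 30 pouches: 13 at Visit 1 and 18 at Visit 2 (8.3.3).

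**Gap between scheduled tests.** The plan's own figure is 6 months.
- Nominal: 365.25 / 2 = 182.6, about 183 days.
- Visit 1 to Visit 2, one movable end: 182.6 ± 10 = 172.6 to 192.6, about 173 to 193 days.
- Visit 2 to Visit 3, two movable ends: 182.6 ± 20 = 162.6 to 202.6, about 163 to 203 days.

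**Does the supply cover the gap?**
- Visit 1: 13 × 30 = 390 pouches; 390 / 2 = 195 days, against at most 193 in window.
- Visit 2: 18 × 30 = 540 pouches; 540 / 2 = 270 days, against at most 203 in window.

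A woman can therefore dose through either interval without returning for product. If a relapse delays Visit 2, the first supply still ends at 195 days of full dosing, so that gap in testing does not become an equally long stretch of dosing. The second supply sets no such limit.

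**What falls inside each interval?**

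| Contact | Interval | Pregnancy test or question listed? |
|---|---|---|
| Month 3 call | Visit 1 to 2 | No; intake only |
| Any planned call | Visit 2 to 3 | None planned |
| Relapse visits (onset, 2 and 6 weeks) | Either, only after a relapse | Not in 10.4; arguably through 9.1.5 |

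The patient diary (8.7) records intake and adverse events, but it is reviewed only at visits, so it does not fill the gap.

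**Effect of a question at the month 3 call.** The call falls at 365.25 / 4 = 91.3 days. From the call to Visit 2 is 91.3 ± 10 = 81.3 to 101.3 days, taking the call at exactly three months. The longest nominal stretch without enquiry in the first half falls from about 183 to about 91 days. The second half has no call to use, so there the remedy rests on an instruction given at Visit 2.

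**The case against.** The case on the other side is substantial.

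- **Unseen text.** Advice on contraception and on reporting pregnancy usually belongs to patient information. Section 16.4 makes the consent form a separate document, and it was not available. A reader might infer that women are left without any contraceptive advice. The documents do not support that; they show only that the protocol text is silent. This part of the objection stands.
- **Relapse visits.** Section 9.1.5 speaks of every visit after baseline, and 10.4 calls its contacts visits. Appendix 1 is headed as a recommended schedule and has no column for unscheduled visits, so its silence is weak evidence. It would be too strong to say that women who relapse go untested. What remains is that 10.4 does not itemise the test, so sites could differ.
- **Dispensing is controlled.** The test precedes dispensing in both lists: items 8 and 14 at Visit 1, and items 5 and 9 at Visit 2. The rule is therefore applied whenever product is handed out. That is correct, but each supply then lasts until the next scheduled visit.
- **No demonstrated harm.** The documents show no specific foetal hazard, do not give the number of women who could become pregnant, and set no shorter testing interval. Six months of dosing is a worst case: conception soon after a visit, no intervening test, and no recognition or report. All of this stands and keeps the point minor.
- **Timing.** The SAP, dated 20/07/2020, describes sixty subjects as already enrolled (4.2). A change to the entry criteria might therefore help nobody, and none is proposed.

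None of this gives a woman without a relapse a planned pregnancy enquiry between scheduled visits.

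**Conclusion.** The point holds as a minor, inexpensive improvement. For a woman without a relapse, the plan leaves nominally 183 days between pregnancy tests (about 173 to 193 days in the first half and 163 to 203 in the second, in window), with enough product to dose throughout and no planned enquiry about pregnancy in between. For a woman who relapses, the answer depends on how 9.1.5 is read, and 10.4 does not settle it.

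This rests on the visible visit lists, on a 6-month interval taken as 182.6 days, and on dosing at two pouches a day. A reader might go further and infer that foetal harm is expected, or use relapse rates to estimate how many women are affected. Neither follows: no hazard is documented, and the frequency of relapse visits says nothing about the frequency of pregnancy. The argument rests only on the sponsor's own exclusion of pregnant women and its stop rule in 9.1.5.

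**What to change.** Use the contacts that already exist.

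1. Add a question about possible pregnancy to the month 3 call, with the instruction to stop the product and be tested if pregnancy is suspected.
2. At Visits 1 and 2, tell women who could become pregnant to report a suspected pregnancy at once. Visit 2 matters most, because no call follows it.
3. Make 10.4 agree with 9.1.5 by listing the dipstick test, or at least the question, at relapse visits.

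The cost is a few minutes of staff time per contact and a short amendment. No visit is added, and endpoints, blinding and sample size are untouched. The change helps only women still on treatment; if none remain, it belongs in a later protocol.
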